Stents themselves are associated with significant patient morbidity that includes pain, blood in the urine, lower urinary tract symptoms (LUTS) and urinary discomfort which can result in an ED visit for evaluation, and sometimes hospitalization because of infection.(5) There has been great interest in the role of silicone as an alternative stent material due to the potential for decreased patient morbidity and encrustation.(11, 12) Bacterial biofilm formation and mineral deposition (encrustation) lead to ureteral wall inflammation, trauma and pain. Prospective clinical studies comparing the use and outcomes of non-silicone stents versus silicone stents is limited, but has demonstrated improvements in stent related morbidity and pain.(12, 13) To date, there have been no studies examining outcomes of silicone ureteral stent placement in the US healthcare system using validated and patient friendly PRO measures, that also assess the downstream consequences of healthcare resources including ambulatory nursing/physician care utilization and unplanned healthcare encounters such as ED visits. Therefore, we propose a comparative effectiveness study to assess outcomes of a standard non-silicone ureteral stent versus silicone ureteral stent placement after URS to understand differences in patient health-related quality of life, morbidity, and its consequences for patients and their caregivers. The pragmatic study design will encourage patient and urologist participation and reduce resource use. Our proposed study will be the first to evaluate the Imajin silicone stent in the United States healthcare system. MUSIC has become an international leader in urological quality improvement and is uniquely situated to provide practical real-world evidence that has the potential to change practice.

No more than minimal increased risk to the participants is expected for the present study. All potential participants are planning to undergo a surgical procedure (URS) with a board-certified urologist trained in URS with stent placement in accordance with AUA guidelines. They will be placing either a non-silicone (standard) ureteral stent or a silicone ureteral stent, both of which are FDA approved.(14, 15) Neither the stent, study protocol, nor manual of operation requires alteration to standard of care.

Section 4.5: Potential Benefits

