Participants at a given performance site who meet all inclusion/exclusion criteria will be randomized using Randomize.net or a similar randomization methodology as endorsed by the Michigan Institute for Clinical & Health Research (MICHR). Subjects will be randomized to either silicone or non-silicone ureteral stent placement at a 1:1 allocation ratio. Blocked, stratified randomization based upon surgeon classified stone location (renal only versus ureteral), with random block sizes will be used to ensure group balance. Randomization list will be determined separately in strata defined by state the stratification factor/s here. The randomization code will be generated by an independent statistician.

At the time of surgery, if baseline PRO has been completed, prior to placement of the stent, the surgeon will be notified via email/text message and the surgeons operating room staff can reference the MUSIC registry to confirm if the patient should have a silicone vs non-silicone stent based on random allocation by the BLUES study coordinator or another member of the BLUES study team. Only patients who are randomized, remain eligible prior to stent placement, and receive the study treatment will be counted towards the treatment population of 224 participants. These patients will receive PRO questionnaires, via the ROCKS PRO infrastructure, pre-operatively and at 7 days, and 4 weeks after surgery. If the patient is unable to complete the PRO questionnaires through the ROCKS PRO infrastructure, the patient may complete an email survey via REDCap, survey by phone from a BLUES study team member, or paper questionnaires. Patients will also receive text messages which include pain-specific questionnaires to be completed daily for 10 days after surgery. The process of completing the ROCKS PRO questionnaire is

the same, regardless of the patient's participation in the BLUES study. A patient can withdraw or decline participation in BLUES and/or ROCKS PRO at any time.

Section 8: TREATMENT PLAN

Section 8.1: Treatment overview

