Adverse event (AE) monitoring and reporting is a routine part of every clinical trial and is done to ensure the safety of subjects enrolled in the studies as well as those who will enroll in future studies using similar agents. Data on adverse events will be collected from the time of the initial study intervention through 30 days after the study intervention. Any serious adverse event that occurs more than 30 days, and before 60 days of the study intervention and is considered related to the study intervention must also be reported. Serious Adverse Events (SAEs) will continue to be followed until:

- Resolution or the symptoms or signs that constitute the serious adverse event return to baseline;
- There is a satisfactory explanation other than the study intervention for the changes observed; or
- Death.

The investigator is responsible for the detection, documentation, grading, and assignment of attribution and expectedness of events meeting the criteria and definition of an AE or SAE. The definitions of AEs and SAEs are given below. It is the responsibility of the principal investigator to ensure that all staff involved in the trial is familiar with the content of this section.

Any medical condition or laboratory abnormality with an onset date before the initial study intervention will be considered pre-existing in nature. Any known pre-existing conditions that are ongoing at the time of study entry should be considered medical history.

For this study, non-serious AEs will not be reported to the IRB. SAEs will be reported in keeping with the governing IRBs guidelines.

Section 10.2: Definitions

1. Adverse Event

For the purposes of this trial, an adverse event (AE) is considered any untoward medical occurrence in a patient receiving study treatment that has or potentially has a causal relationship with this treatment. Any untoward medical occurrences that are unrelated to the study intervention will not be considered adverse events.

Symptoms of kidney stone disease and expected side effects from ureteroscopy lithotripsy and stent placement are not considered adverse events for this study. The following symptoms are indicative of underlying kidney stone disease and expected side effects from ureteroscopy with laser lithotripsy and stent placement, and will not be reported as adverse events (unless the event meets the criteria of an SAE):

- Hematuria
- Irritative voiding symptoms (e.g., urinary frequency, urgency, dysuria)

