An adverse event (AE) is considered "unexpected" if it meets the criteria of an AE per section 10.2, and is not expected as described above.

Section 10.3: Reporting of Unanticipated Problems

Upon becoming aware of any incident, experience, or outcome (not related to an adverse event) that may represent an unanticipated problem, the investigator should assess whether the incident, experience, or outcome represents an unanticipated problem. The incident, experience or outcomes is considered unanticipated if it meets all of the following criteria:

1. Unexpected (in terms of nature, severity, or frequency);
2. Related or possibly related to participation in the research; and
3. Suggests that the research places subjects or others at a greater risk of harm than was previously known or recognized.

If the investigator determines that the incident, experience, or outcome represents an unanticipated problem, the investigator must report it to the IRB according to the local IRB policies.

Section 10.4: Unblinding Procedures

To minimize bias in patient-reported outcome measures, all reasonable efforts will be made to keep patients blinded to their randomized treatment allocation. This will help to assure that all patient-reported outcomes and clinical data collection for the trial have been completed prior to unblinding. Patients will be notified of their randomized treatment allocation by trial staff at the coordinating center at the conclusion of the study.

In the case of a medical emergency or other event in which the participant's knowledge of their treatment allocation is critical to the participant's clinical management, the blinding for that participant may be broken by the investigator. The investigator or their designee must document the date and reasons for such emergency unblinding in the participant's source documents. The investigator must also immediately notify the study PI and trial coordinating center of such an event.

Section 10.5: Stopping Rules

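### Adverse events are recorded only if judged possibly related to treatment, by an investigator who is not described as blinded; relatedness should be a recorded field, not a condition of entry

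*Combined protocol and SAP*

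**What the plan says.** Section 10.2, item 1, limits adverse events to those for which the occurrence "has or potentially has a causal relationship with this treatment", and adds: "Any untoward medical occurrences that are unrelated to the study intervention will not be considered adverse events". Item 2 defines a serious adverse event as an adverse event with one of several outcomes, in the investigator's view. It also leaves out hospital visits for conditions not associated with the stone. Section 10.1 collects adverse events for 30 days after the intervention. From then until day 60 it asks only for serious events considered related.

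On who decides, Section 10.1 states: "The investigator is responsible for the detection, documentation, grading, and assignment of attribution and expectedness of events". No blinded or independent adjudication is described.

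On who knows the arm, Section 10.4 says that "all reasonable efforts will be made to keep patients blinded to their randomized treatment allocation" and names nobody else. In Section 7, "prior to placement of the stent, the surgeon will be notified via email/text message", and operating room staff can check the allocation in the registry. Section 8.2 has the size, brand and name of the stent documented in the operative report.

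Section 11.3 defines a Safety Population of randomized patients who receive a stent, analyzed by assigned arm. Section 11.4 gives no method for summarizing or comparing adverse events.

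Item 1 also lists symptoms, hematuria among them, that "will not be reported as adverse events (unless the event meets the criteria of an SAE").

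**The concern.** Relatedness is normally something recorded about an event. Here it decides whether the event exists in the adverse event data at all, and it is judged by someone who can know the arm in a trial whose stated hypothesis is that silicone is superior. If an investigator more readily blames one stent than the other for the same fever or infection, the recorded counts differ by arm although the true rates do not. An event that was never entered cannot be re-adjudicated later, so the distortion cannot be undone in analysis. The adverse event reports discussed with the monitoring committee (Section 12) pass through the same filter.

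A second problem is that the boundary of the definition is unclear, so the six practices could code the same event differently even with no preference between stents.

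**Working it through.** The plan states no adverse event rate, safety margin or safety power, so there is no figure to reproduce. The check is mainly of the text, with an illustration on assumed values.

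**1. Does the condition reach serious events?** Yes. Item 1 requires at least potential relatedness for an adverse event, and item 2 builds the serious event on the adverse event. The stone-related restriction on hospital visits is a further filter, tied to the stone although the randomized factor is the stent.

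**2. Can the attributing investigator know the arm?** Yes. The surgeon is told before placement, and anyone reading the operative report can see the stent's name. The documents do not say that the attributing investigator is always the operating surgeon, so the supportable statement is that the investigator can know the arm.

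**3. Related to what?** Three places, side by side:
- Section 2 defines the study intervention as insertion of the stent at the end of ureteroscopy.
- Section 10.2, item 1, says expected side effects of ureteroscopy with lithotripsy and of stent placement are not adverse events.
- Section 10.2, item 3, lists known risks of anesthesia and ureteroscopy (for example urinary infection, fever, sepsis, acute kidney injury, myocardial infarction) as expected adverse events, provided they already meet the adverse event criteria.

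Item 3 makes little sense unless events due to the procedure can count. Item 1 together with Section 2 can be read to exclude them.

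**4. How does the mechanism work?** Recorded rate = true rate × probability that an event is judged at least potentially related. With the same true rate r in both arms and attribution probabilities a₁ (non-silicone) and a₂ (silicone), the apparent risk ratio is (r·a₂)/(r·a₁) = a₂/a₁. The true rate cancels. If a₁ = a₂ the ratio is 1.0 and there is no bias.

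Expected recorded events with 112 per arm (Section 11.2), where r, a₁ and a₂ are all assumptions:

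| True rate, both arms | a₁ = 90%, a₂ = 70% | a₁ = 80%, a₂ = 50% |
|---|---|---|
| 10% | 10.1 vs 7.8 | 9.0 vs 5.6 |
| 20% | 20.2 vs 15.7 | 17.9 vs 11.2 |
| 30% | 30.2 vs 23.5 | 26.9 vs 16.8 |
| Apparent risk ratio | 0.70/0.90 = 0.78 | 0.50/0.80 = 0.625 |

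Example: 112 × 0.20 × 0.90 = 20.2 and 112 × 0.20 × 0.70 = 15.7. The direction is also assumed. If silicone events were attributed more readily, the ratios would be 0.90/0.70 = 1.29 and 0.80/0.50 = 1.60.

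**5. What escapes the filter?** PROMIS pain, daily text-message pain, LURN SI-10, 30-day utilization and new or worsening hydronephrosis are compared by arm with no attribution condition stated (Sections 5.4 and 11.4). Utilization is graded by type of contact, not by cause: an infection handled by telephone appears only as a telephone contact. None of these measures identifies an infection or a fever as such.

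**6. Hematuria.** Section 4.3 lists it as a stent risk, and Section 4.4 says: "Stents themselves are associated with significant patient morbidity that includes pain, blood in the urine". It is not recorded as an adverse event unless serious, and no item in the Figure 1 questionnaires asks about it.

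**The case against.** The strongest defense is that this is a pragmatic comparison of two approved devices used in usual care, with minimal added risk expected, and that limited adverse event collection is a deliberate choice. The threshold is low, since potential relatedness is enough. Pain, urinary symptoms, hospital and emergency use, and hydronephrosis are all compared without the filter. Comparing adverse events is not a stated objective, and no method for it is given. All of this stands, and it limits the point. It does not remove it: a Safety Population analyzed by arm implies a summary by arm, and the unfiltered endpoints do not say which events occurred.

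Several stronger readings are tempting, and the documents do not support them:
- *Named stent harms are excluded outright.* The listed symptoms remain reportable if serious, and stent migration and encrustation are listed as expected adverse events.
- *The whole safety comparison is filtered by opinion.* Only the adverse event and serious adverse event data are.
- *An infection blamed on the ureteroscopy is lost.* Item 3 points the other way; the text is ambiguous.
- *The symptom list biases the comparison.* It applies equally to both arms, so it loses information without favoring either.
- *Silicone would show a false reduction of a given percentage.* Any such figure only restates the assumed attribution probabilities. Even on the assumptions above, the chance that a test at the two-sided 5% level would call the difference significant runs only from about 8% to 40%.

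**Conclusion.** The point holds as a correctable weakness in the adverse event definition. Entry into the adverse event and serious adverse event data depends on a judgment by an investigator who can know the arm, and counts by assigned arm can be distorted if that judgment differs by arm. Whether it would differ, in which direction and by how much cannot be derived from the documents. The ratios of 0.78 and 0.625 show the mechanism on assumed values and are not estimates for this trial. The primary pain analyses are unaffected.

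Separately, Section 10.2 items 1 and 3 and the definition of the intervention in Section 2 do not settle whether procedure-related events count.

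The gap on non-serious hematuria is a secondary matter: information is lost, but no bias between arms follows from it.

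**What to change.** In Section 10.2, item 1, define the recorded event as any untoward medical occurrence from stent placement to the end of adverse event collection, whatever its attribution. If that is too broad for a pragmatic trial, record at least the events listed in item 3 and all hospitalizations. Add two case report form fields, one for relatedness to the stent and one for relatedness to the ureteroscopy. State in Section 11.4 that all events are summarized by arm first and related events second. Reconcile items 1 and 3 with the definition of the intervention in Section 2.

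The cost is protocol and form wording plus more non-serious rows to enter. Forms are already completed on the operative day, at stent removal, and for the day 30 and day 60 assessments (Section 9), and IRB reporting rules can stay as they are.

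Optionally, capture hematuria that leads to an unscheduled contact. This needs the reason for contact, which the documents do not say is collected, so it is a real addition and should come second.

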A ureteral stent is a flexible, small, hollow tube measuring 24-30 cm in length that sits between the bladder and kidney, and permits drainage of urine from the kidney. Ureteral stents are FDA approved devices and widely available as guideline recommended care for ureteroscopy. Stents are designed and utilized to avoid adverse events and unplanned operations after URS such as for urinary obstruction or sepsis.(8) Stent placement is recommended after URS in many clinical scenarios for a temporary period of time permitting drainage of urine from the kidney. There are specific indications for stent use, and not all patients require it. American Urological Association (AUA) guidelines recommend stent placement for patients undergoing ureteroscopy with ureteric injury, evidence of ureteral obstruction, a large stone burden (>1.5 cm), a solitary kidney, renal functional impairment, and in those in whom another ipsilateral procedure is planned.(8) Urologists report placing ureteral stents routinely in approximately 80% of all cases.(9) The risks of stents include: infection, encrustation, obstruction, rupture, migration, bladder irritation symptoms, pain, hematuria, erosion. Following placement, the stent is often removed 1-3 weeks later by the urologist in the office.

In MUSIC, we recently performed an extensive RAND/UCLA Appropriateness Method process involving 15 diverse urologists across Michigan to define uncomplicated URS in real-world practice and provide information on clinical scenarios appropriate for stent omission (Appendix 1). During this process it was clear that very few urologists would consider stent omission for larger stones (i.e. stones 1-1.5 cm in size) regardless of its location (renal or ureteral) (dark red bars in Appendix 1), or even for smaller stones, if a device during surgery called the ureteral access sheath (UAS), was used (light red bars in Appendix 1). The UAS is used in 37% of URS cases in Michigan.(10) We also learned from this process that many urologists would opt for stent omission if the patient was pre-stented, i.e. having a stent already in place at the time of surgery because it was placed as an emergency in patients with ureteral colic and obstruction. This process in MUSIC has provided us real-world information that allowed us to design a clinical study with appropriate inclusion criteria that can optimally assess the benefits of ureteral stenting in clinical practice.

Section 4.4: Justification

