- Abdominal/flank/bladder pain
- Nausea and/or vomiting
- Dizziness and lightheadedness
- Urinary retention

Abnormal laboratory values or test results constitute adverse events only if they induce clinical signs or symptoms or require therapy. They are to be captured under the signs, symptoms, or diagnoses associated with them.

2. Serious Adverse Event

An adverse event is considered “serious” if, in the view of the investigator, it results in any of the following outcomes:

- Death
 - If death results from (progression of) the disease, the disease should be reported as an event (SAE) itself.
- A life-threatening adverse event

- An adverse event is considered 'life-threatening' if, in the view of either the investigator [or sponsor], its occurrence places the patient or subject at immediate risk of death. It does not include an adverse event that, had it occurred in a more severe form, might have caused death.
- Inpatient hospitalization or prolongation of existing hospitalization for > 24 hours.
- A persistent or significant incapacity or substantial disruption of the ability to conduct normal life functions
- A congenital anomaly/birth defect
- Important medical event
 - Any event that may not result in death, be life-threatening, or require hospitalization may be considered serious when, based upon appropriate medical judgment, they may jeopardize the patient and may require medical or surgical intervention to prevent one of the outcomes listed in this definition of "Serious Adverse Event". Examples of such medical events include allergic bronchospasm requiring intensive treatment in an emergency room or at home; convulsions that do not result in inpatient hospitalization or the development of drug dependency or drug abuse.

Hospital visits for conditions not associated with the urinary stone will not be collected or reported as SAEs.

3. Expected Adverse Event

An adverse event (AE) is considered "expected" if it meets the criteria of an AE per section 10.2, and is a known risk of general anesthesia and ureteroscopy such as:

- Myocardial infarction, deep vein thrombosis, cerebrovascular accident, pulmonary embolism, fever, UTI, sepsis, perinephric hematoma, acute kidney injury, ureteral injury or perforation, ureteral stricture or scarring, stent migration or dislodgement, stent encrustation

4. Unexpected Adverse Event

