In addition to the WinRatio, our second composite analysis will include healthcare utilization and PROMIS® Pain. Additionally, we will use a composite score ranking of healthcare utilization similar to the WinRatio plan and add the PROMIS® Pain scores to the analysis using DOOR. The probability that a randomly selected patient will have a better DOOR if assigned to the silicone stent will be estimated.(21) The WinRatio and DOOR composite healthcare utilization metric ratios' sizes and directions will be compared.

The number and proportion of patients who are prescribed opioid medications will be reported by arm and compared using a chi-square test.

Satisfaction score assessed using the ICIQ-S will be summarized at 7 days and 4 weeks by arm with means and standard deviations. A repeated measures model will be used to test if satisfaction differed at either time between treatment arms using an interaction of time and arm.

Section 12: DATA AND SAFETY MONITORING

The DSMC will consist of the MUSIC ROCKS Program Manager, Program Director, Statistician, and other members of the MUSIC ROCKS team. This committee is responsible for monitoring the safety and data integrity of the study.

Each performance site's local study team is required to meet virtually with the DSMC and BLUES study team every six months if it is determined by the DSMC and/or Principal Investigator that a virtual meeting is necessary. The discussion may include matters related to the safety of study participants (Serious Adverse Event, Adverse Event and Unanticipated Problem reporting), completeness, validity and integrity of the study data, enrollment rate relative to expectations, characteristics of participants, retention of study participants, and adherence to the protocol (potential or real protocol deviations). If there are no concerns around any of the aforementioned items, the principal investigator and/or the DSMC may decide that a meeting is unnecessary and if so, a progress summary communication will serve in its place. Additionally, a member of the BLUES study team will send a communication summarizing current progress to each site on a monthly basis. These communications will consist of 1) any identified Serious Adverse Events and necessary follow-up, 2) enrollment rate relative to expectations, and 3) any identified protocol deviations, unanticipated problems, and recommendations to prevent additional instances.

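### A related, non-serious adverse event that signals new risk has no required report to the IRB or DSMC, because Section 10.3 excludes AE-related matters and Section 10.1 reports only serious events

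*Combined protocol and SAP*

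**What the plan says.** Four parts of the combined protocol and SAP bear on this point.

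- **Section 10.1** has AE data collected through 30 days after the intervention and makes the investigator responsible for grading, attribution and expectedness. On reporting it says "For this study, non-serious AEs will not be reported to the IRB" and "SAEs will be reported in keeping with the governing IRBs guidelines".
- **Section 10.2** counts an occurrence as an AE only if it has, or may have, a causal link to study treatment. It separates expected from unexpected AEs, and the expected kind "is a known risk of general anesthesia and ureteroscopy such as" the examples it then lists. Neither label leads to any reporting step.
- **Section 10.3** starts the unanticipated-problem assessment with "Upon becoming aware of any incident, experience, or outcome (not related to an adverse event) that may represent an unanticipated problem". Three criteria follow: unexpected in nature, severity or frequency; "Related or possibly related to participation in the research; and" suggestive of greater risk than was previously recognized. If all three are met, "the investigator must report it to the IRB according to the local IRB policies".
- **Section 12** makes AE reporting a permitted topic of six-monthly meetings. It lists the content of the monthly communication to sites: "These communications will consist of 1) any identified Serious Adverse Events and necessary follow-up", then enrollment, then deviations, unanticipated problems and recommendations. The study team's onward reporting covers SAEs, unanticipated problems and deviations.

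**The concern.** An unanticipated-problem rule exists to bring new risk to the IRB while a trial is running. In a comparison of two device types, much of that risk would first appear as adverse events. Section 10.3 removes AE-related matters from the assessment before its criteria are applied, and Section 10.1 sends only the serious ones to the IRB by another path. The events left over are non-serious, related, and more frequent or different in kind from what was expected.

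At stake is timely notice of a pattern, such as a run of non-serious stent complications during enrollment. The statistical plan offers no substitute. The stopping rule in Section 10.5 concerns PROMIS pain scores only. Section 11.3 defines a safety population, but Section 11.4 describes no analysis of adverse events.

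**Working it through.** The plan gives no figure on this point, so no arithmetic applies. The check follows one type of event through every reporting provision. The event is an AE under Section 10.2, is non-serious, is unexpected in nature, severity or frequency, and suggests greater risk than was known.

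| Provision | Does it require a report to the IRB or DSMC? |
|---|---|
| Section 10.1, non-serious AEs | No; IRB reporting is expressly ruled out |
| Section 10.1, SAEs | No; the event is not serious |
| Section 10.2, unexpected AE | No; the label carries no action |
| Section 10.3, unanticipated problem | No; the event is AE-related, so the assessment does not begin |
| Section 12, six-monthly meeting | No; AE reporting is a topic that may be covered, and the meeting may be replaced by a progress summary if there are no concerns |
| Section 12, monthly communication | No; it goes to sites and does not list non-serious AEs |
| Section 12, onward reporting | No; limited to SAEs, unanticipated problems and deviations |

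Required reports to the IRB or DSMC: none. The mandatory steps are collection of the AE data and the investigator's grading and attribution.

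Next, does the exclusion fit Section 10.3's own criteria?

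1. Criterion 2 asks for a related or possibly related event. Section 10.2 already builds an actual or potential causal link to treatment into the definition of an AE, so an AE will nearly always meet this criterion. The parenthesis thus removes the class of events most likely to satisfy it.
2. Criterion 1 includes unexpected frequency. An excess of non-serious events that Section 10.2 lists as expected, such as stent migration or encrustation, could therefore meet it. Those events are AEs too, so they are also excluded.

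Last, what lies outside the gap?

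- A malfunction with no untoward medical occurrence is not an AE under Section 10.2, so it remains within Section 10.3.
- An event judged an important medical event under Section 10.2 is an SAE and is reportable under Section 10.1.
- The urinary and pain symptoms that Section 10.2 says are not AEs (unless serious) are not caught by the exclusion.

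**The case against.** The strongest reply is that the parenthesis only sorts incidents: AEs are handled in Sections 10.1 and 10.2, everything else in Section 10.3. That is a plausible drafting intent. But Section 10.1 then has no counterpart for an unexpected, related, non-serious AE, so the two sections need reconciling on either reading.

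A second reply is that withholding non-serious AEs from the IRB is a deliberate choice in a pragmatic trial of marketed, FDA-approved stents with at most minimal added risk. That is reasonable for routine events. It does not explain why an event meeting all three of Section 10.3's criteria should be left out. Local IRB policy does not clearly fill the gap either, because Section 10.3 invokes it only after an event has been judged an unanticipated problem.

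Other replies stand, and they rule out stronger readings that a reader might infer.

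- **That nobody outside the site learns of such an event.** The documents do not support this. The Time and Events Table in Section 9 schedules a case report form at stent removal and safety follow-up to days 30 and 60. Under Section 14 the central team reviews study-specific registry data and meets at least monthly, although the stated aim is protocol adherence. The program manager and a statistician are named in both the study team (Section 7) and the DSMC (Section 12).
- **That the six-monthly meeting can simply be waived.** Section 12 allows this only when there are no concerns about the listed items, which include AE reporting, and a progress summary must take its place.
- **That a stent breaking at removal would certainly go unreported.** Without clinical harm it may be a malfunction still covered by Section 10.3. If it needs intervention, it may be judged an SAE. The important-medical-event clause is discretionary, however, so it does not close the gap.
- **That particular stent failures are wrongly classed as unexpected.** Section 4.3 says "The risks of stents include: infection, encrustation, obstruction, rupture, migration, bladder irritation symptoms, pain, hematuria, erosion", and some of these are absent from the expected list in Section 10.2. But that list is open-ended, other items appear in the separate symptom list, and neither label triggers a report. Since rupture is a recognized risk, a single rupture might not meet the third criterion anyway.

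**Conclusion.** The point holds in a limited form. As written, Sections 10.1, 10.3 and 12 require no report to the IRB or DSMC of a related, non-serious AE that is unexpected in nature, severity or frequency and suggests greater risk than was known. This is a stated exclusion that works against Section 10.3's own criteria, rather than a detail left out.

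The gap is one of escalation. The data are collected, reach the registry and may be discussed. How often such an event would arise cannot be estimated from the documents, so no size in patients or events is attached. The conclusion assumes that the parenthesis means what it says and that no manual or local policy outside these documents adds a duty. Sample size, error rates and efficacy analyses are untouched.

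**What to change.** 1. In Section 10.3, delete the parenthesis that removes AE-related matters, so that AEs are assessed against the same three criteria as other incidents.
2. In Section 10.1, state that the sentence on non-serious AEs does not apply to an event meeting those three criteria. Without this, the two sections would contradict each other once the parenthesis is gone.
3. In Section 12, add to the monthly communication a count of related non-serious AEs, pooled across arms and whether or not listed as expected. A line limited to unexpected events would miss an excess of listed ones, and would lose any event later added to the expected list. Because that communication is addressed to sites, copy the line to the DSMC.

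Pooling is advisable because the communication goes to sites, and because the overlap between the DSMC and the study team means a by-arm table could not readily be confined to the DSMC. The price is that a pooled count shows an unexpected overall frequency but not which arm it comes from.

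The cost is wording in three sections, a few additional investigator assessments and one line in an existing communication. Design, sample size and patient care do not change.
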